4. STUDY DESIGN

4.1. Overall Design

This study will compare the efficacy, safety, and tolerability of 2 dosing regimens of rodatristat ethyl to placebo in patients with PAH over a 24-week treatment period. Investigational product (IP) will be administered on the background of stable PAH therapy.

Protocol RVT-1201-2002

Effective: 19JAN2022

Approximately ninety (90) patients will be enrolled. Patients will be randomized 1:1:1 to placebo, 300 mg BID, or 600 mg BID of rodatristat ethyl.

Eligible patients will be stratified based on the number of background PAH therapies they are receiving (1 vs 2 vs 3) and selexipag use (Yes/No). The number of patients who are on a prostanoid infusion will be capped at 50% of the total enrolled. The number of patients who are receiving selexipag will be capped at 20% of the total enrolled.

The study will consist of a Screening Period (up to 28 days in duration), a Baseline Period (Day 1), a 24-week Treatment Period (Main Study), and for patients that early terminate or do not enroll an Open-Label Extension (OLE), and a 4-week Follow-Up Period (approximately 4 weeks after the last dose), for a total study duration of 32 weeks.

Patients who complete the Main Study will have the option to enroll into an OLE and continue to receive rodatristat ethyl (those randomized to placebo will be re-randomized 1:1 to receive rodatristat ethyl 300 mg BID or 600 mg BID) for 6.5 years, until the Investigator or patient chooses to stop the IP, any stopping criteria in the Main Study are met, IP becomes commercially available, or the Sponsor stops the study for lack of efficacy or a safety signal (whichever preceding criteria comes first). In no case will a patient be allowed to exceed 10 years of exposure unless the product is approved for a chronic indication.

All participating patients will be required to be on a stable background therapy for PAH with mono, dual or triple combination therapy (which may include currently approved prostanoid therapies) at the time of Screening. All patients will maintain their standard of care (SOC) regimen at entry for the duration of the study. Refer to Section 6.6.2 for more details.

During the 24-week Treatment Period, in addition to the Day 1/Baseline Visit and a telemedicine or phone call at Weeks 2 and 8, patients will return to the study center for safety, tolerability and efficacy-related assessments at Weeks 4, 12, and 24, and a clinic or home visit at Week 18, as specified in the Schedule of Events Table, Section 1.3, as well as Follow-up at Week 28 (as applicable). Female patients of childbearing potential will undergo pregnancy testing every 4 weeks and will be required to use 2 reliable methods of contraception to reduce the risk of pregnancy, at Screening, during the course of the study, and for at least 4 weeks following the last dose of rodatristat ethyl. Additional pregnancy testing in women whose menstruation is delayed or who have infrequent or irregular menstrual cycles should be completed as warranted.

Further details for the OLE are found in Section 7.

4.2. Number of Patients

Approximately ninety (90) patients with PAH are expected to be enrolled at approximately 68 study sites in the United States, Canada, and Rest of World (ROW).

4.3. Treatment Assignment

Patients will be randomized to IP according to a computer-generated allocation schedule, prepared prior to the start of the study.

At the Baseline Visit, eligible patients will be randomly allocated (1:1:1) to one of the following 3 treatment groups:

Treatment Arm Name	Treatment Description
Rodatristat ethyl 300 mg BID	1 x 300 mg tablet + 1 x matching placebo BID
Rodatristat ethyl 600 mg BID	2 x 300 mg tablets BID
Placebo	2 x matching placebo tablets BID

In order to maintain the study blind, patients will take 2 tablets in the morning and 2 tablets in the evening in one of the combinations noted above.

4.4. Dose Adjustment Criteria

4.4.1. Dose Reduction

All determinations of rodatristat ethyl dose reduction should be discussed with the Medical Monitor prior to implementing unless time does not allow for safety.

Temporary dosage reductions or discontinuations will be allowed to manage AEs/AESIs (or other instances to be discussed with the Medical Monitor), including gastrointestinal AEs (e.g., diarrhea, nausea, or vomiting) or liver enzyme increase occurring during the 24 weeks of the study. Judicious use of antidiarrheal and/or anti-emetic medications will be permitted. One level of dose reduction is available.

To reduce the IP, the patient will be instructed to take one tablet in the morning and one tablet in the evening from the appropriate dispensed bottles during the dose reduction period per dosing instructions supplied in a separate document. If AEs continue, the patient may stop taking the IP completely for up to 7 days before restarting.

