- Matching placebo BID (2 x placebo BID)

In order to maintain the study blind, all patients will receive 2 tablets of either rodatristat ethyl and/or placebo in the morning and in the evening in one of the combinations noted above.

Temporary dosage reductions or discontinuations will be allowed to manage adverse events (AEs)/Adverse events of special interest (AESIs), including gastrointestinal AEs (e.g., diarrhea, nausea, or vomiting) and liver enzyme elevations occurring during the 24-week treatment period. Use of antidiarrheal and/or anti-emetic medications will be permitted as directed by the Investigator.

Patients randomized to a rodatristat ethyl arm in the Main Study may continue at the dose level given during the Main Study in the OLE. Patients randomized to placebo in the Main Study will be rerandomized to one of the active rodatristat ethyl treatment arms (300 mg BID or 600 mg BID) during the OLE. Changing of treatment for all patients in the OLE, to receive either 300 mg BID or 600 mg BID, could depend on the timing and outcome of the 24-week analysis from the Main Study. Tolerability and all accumulated safety and efficacy data will be reviewed by the Independent Data Monitoring Committee (IDMC) at regular intervals.

Non-Investigational Therapies:

Patients will remain on their prescribed, pre-existing background PAH medications; doses of these medications should remain stable during the study. All treatment modifications (changes in dose or regimen) will be documented.

Any changes to background PAH therapy during the study should be based on clear medical need and should be first discussed with the Medical Monitor whenever possible.

tavant Sciences GmbH Effective: 19JAN2022

Protocol RVT-1201-2002

Statistical methods:

A detailed description of statistical methods will be provided in a separate Statistical Analysis Plan (SAP) that will be finalized prior to database lock.

Sample Size Justification:

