6.1. Description of IP

The IPs to be administered as part of this study are described in Table 3.

Table 3: Investigational Products

Arm Name	300 mg BID*	600 mg BID*	Placebo*
Dose Formulation	Tablet	Tablet	Tablet
Unit Dose Strength(s)	300 mg	300 mg	N/A
Dosage Level(s)	1 x 300 mg tablet + 1 x placebo tablet BID	2 x 300 mg tablets BID	2 x placebo tablets BID
Route of Administration	Oral	Oral	Oral
IP	Rodatristat ethyl	Rodatristat ethyl	Placebo
Physical Description	White to off-white modified oval shaped tablet, debossed with "2E8" on one side		
Manufacturer	Patheon Pharmaceuticals [name] Canada		
Packaging and Labeling	IP will be provided in bottles. Each bottle will be labeled as required per country requirement.		

^{*}The components in rodatristat ethyl are provided in Section 3.2.2, Table 1 of the Investigator's Brochure. The active and placebo are formulated with the same excipients.

Abbreviations: BID = twice daily; IP = investigational product; N/A = not applicable

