7.9. Open-Label Extension Treatment Assignment

At the Screening/Enrollment Visit of the OLE, eligible patients who received placebo during the main study will be randomly allocated (1:1) to one of the following 2 treatment groups:

Treatment Arm Name	Treatment Description
Rodatristat ethyl 300 mg BID	1 x 300 mg tablet BID
Rodatristat ethyl 600 mg BID	2 x 300 mg tablets BID

Abbreviation: BID = twice daily

Patients who received active IP while in the Main Study may remain on the same active dose in the OLE or may be provided with a new dose of IP to receive either 300 mg BID or 600 mg BID depending on the timing and outcome of the 24-Week analysis from the Main Study.

Tolerability and all accumulated safety and efficacy data will be reviewed by the Independent Data Monitoring Committee (IDMC).

IP will be supplied without placebo. The first dose of IP in the OLE will be considered the first dose after all Week 24 assessments in the Main Study are completed and all entry criteria met.

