7.11. Dose Adjustment Criteria

Dose adjustment criteria are the same as the Main Study and can be found in Section 6.

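### In the OLE, the only dose-reduction step (one tablet twice daily) changes nothing for patients on 300 mg BID, because that dose is already one tablet twice daily without placebo

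*Protocol*

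**What the plan says.** Protocol 4.4.1 defines the reduction for the Main Study. It states that "One level of dose reduction is available", and that to apply it "the patient will be instructed to take one tablet in the morning and one tablet in the evening", using the appropriate bottles and dosing instructions held in a separate document. In the Main Study every patient takes two tablets per dose; Table 3 in Section 6.1 gives the 300 mg arm as "1 x 300 mg tablet + 1 x placebo tablet BID".

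Two appendices use this step. Appendix 3 (liver) offers one pill twice daily or interruption for ALT/AST from 3 to below 5 times ULN. It also calls for resumption at the lower dose after an interruption at that grade, or after an elevation of 5 to below 8 times ULN that has settled. Appendix 2 (diarrhea) calls for interruption and then a lower dose for Grade 2 lasting 48 hours or more and for Grade 3, and the Grade 4 row refers back to Grade 3. Permanent discontinuation follows when Grade 3 recurs despite symptomatic treatment and dose reduction.

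For the OLE, Section 7.11 says only this: "Dose adjustment criteria are the same as the Main Study and can be found in Section 6". Section 7.9 gives the low dose as "1 x 300 mg tablet BID" and adds that "IP will be supplied without placebo".

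**The concern.** The reduction step was written for a blinded two-tablet regimen. Section 7.11 carries it into an open-label regimen where the low dose is already one tablet twice daily. A site that applies it to an OLE patient on 300 mg BID tells the patient to take what the patient already takes.

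Diarrhea and hepatic enzyme elevations are both listed as adverse events of special interest in Section 9.3.1, so these tables deal with anticipated risks. Former placebo patients assigned 300 mg BID meet the drug for the first time in the OLE. Treatment there may last 6.5 years, and after the first 24 weeks the scheduled laboratory visits are 24 weeks apart (Section 1.5). A written rule that works for both OLE doses is therefore worth having.

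**Working it through.** **Inputs.** Active tablet strength is 300 mg, the only one listed (6.1, Table 3). OLE regimens are one or two 300 mg tablets twice daily without placebo (7.9). The reduction step is one tablet twice daily (4.4.1, Appendix 3).

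**Formula.** Daily dose = active tablets per dose × 300 mg × 2 doses.

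**Plan's own figure.** OLE 300 mg BID: 1 × 300 × 2 = 600 mg/day, which agrees with the label of the arm.

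**Before and after the step**

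| OLE group | Before (mg/day) | After one tablet BID (mg/day) | Change |
|---|---|---|---|
| 600 mg BID | 2 × 300 × 2 = 1200 | 1 × 300 × 2 = 600 | −50% |
| 300 mg BID | 1 × 300 × 2 = 600 | 1 × 300 × 2 = 600 | 0% |

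**What the tables then mean for OLE 300 mg BID**

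| Event | Instruction | Effect for this group |
|---|---|---|
| ALT/AST 3 to <5× ULN | Reduce to one pill BID, or interrupt | Reducing is continuing unchanged; interrupting works |
| Same, resuming after interruption | Resume at the lower dose | Cannot be carried out |
| ALT/AST 5 to <8× ULN, below 3× ULN after 2 weeks | Resume at the lower dose | Cannot be carried out |
| Diarrhea Grade 2 (48 hours or more), Grade 3 or Grade 4 | Interrupt, then lower dose | Interruption works; the lower dose does not exist |
| Recurrent Grade 3 diarrhea | Stop permanently if it recurs despite reduction | The condition presupposes a reduction this group cannot have |

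**The link to the OLE.** Section 4.4.1 speaks of events in the 24 weeks of the study, so 7.11 is the only text that extends the step to the OLE. Its pointer is also wrong: Section 6 contains no reduction criteria. They are in Section 4.4 with Appendices 2 and 3.

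**How many patients are on this dose.** With 30 per arm, full rollover and no switching:
- If the active arms keep their dose (7.4): 30 + 30/2 = 45.
- If everyone is re-randomized (6.4), assuming equal allocation: 90/2 = 45.
- On either reading, about 30/2 = 15 of the 45 come from placebo.
- At assumed rollover of 80% and 70%: 45 × 0.8 = 36 and 45 × 0.7 = 31.5.

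These counts do not hold if doses are switched. Section 7.9 says that patients from the active arms "may be provided with a new dose of IP to receive either 300 mg BID or 600 mg BID", and the Synopsis says "Changing of treatment for all patients in the OLE, to receive either 300 mg BID or 600 mg BID, could depend on" the 24-week analysis. The number on 300 mg BID could then be anything from none to all who roll over. The documents give no rate of Grade 2 or higher events at 300 mg BID, so the number who would need a reduction cannot be estimated.

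**The case against.** The strongest reply is that little turns on this. Sections 4.4.1.1 and 4.4.1.2 describe both tables as management recommendations, and the title of Appendix 3 calls its actions suggested. The Grade 2 liver row gives interruption as an equal choice for the investigator. Reductions should be discussed with the Medical Monitor unless urgency prevents it. The mandatory stopping rules in Section 8 reach the OLE through 7.12 and do not depend on a lower dose, and Appendix 3 itself requires permanent discontinuation if ALT/AST is 3 times ULN or more at 2 weeks or later. All of this stands, and it limits the harm. It does not make the reduction step work, and none of it says what happens at restart for a patient with no lower dose.

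A second reply is that the separate dosing instructions may cover the OLE. They are not among the documents, so this cannot be excluded. Section 4.4.1 cites them for carrying out the same one-tablet step, however, and the protocol should not rely on another sheet to override it.

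Two stronger readings are tempting, and the documents do not support them:
- **That the protocol directs these patients to restart at the dose on which the event occurred.** It does not. Appendix 3 calls for a lower dose, and a restart at 300 mg BID does not follow that text either. The instruction is unworkable for this group, and an unchanged restart is only one way a site might resolve it.
- **That the SAP confirms no lower OLE dose is foreseen,** because Section 8.2.2 lists only 0 mg/placebo or 300 mg as reduced doses. SAP Section 1 leaves the OLE to a separate SAP, so this list says nothing about it.

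**Conclusion.** The point holds as a narrow gap in a stated safety rule and should be fixed. In the OLE, one tablet twice daily is a 50% reduction for 600 mg BID and no reduction for 300 mg BID. For the lower dose, choosing to reduce is the same as continuing, and the instructions to resume at a lower dose cannot be followed.

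The conclusion rests on the protocol wording alone: 7.11 read as carrying 4.4.1 and the appendices into the OLE despite its wrong pointer, a single tablet strength, and no contrary instruction in the separate dosing document. The dose arithmetic is certain on those terms; the clinical consequence is not, because no event rate is available and several safeguards remain. A reader might infer a threat to the trial's results. There is none: the gap concerns the OLE only, and Main Study power and the primary PVR analysis are unaffected.

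**What to change.** In 7.11 and Appendices 2 and 3, state for the OLE that:

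1. One tablet twice daily is a reduction only for patients on 600 mg BID, who go to 300 mg BID.
2. 300 mg BID has no lower level, so wherever the tables say to reduce, treatment is interrupted.
3. Where the tables call for restart at a lower dose, any restart of a 300 mg BID patient is decided with the Medical Monitor, under the monitoring already set out.
4. For this group, the Grade 3 diarrhea recurrence rule applies without a prior dose reduction.

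Correct the cross-reference in 7.11 from Section 6 to Section 4.4 and Appendices 2 and 3, and bring the separate dosing instructions into line if they cover the OLE.

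The cost is a few sentences; no new tablet strength or visit is needed. The downside is small: some 300 mg BID patients will interrupt treatment where they would otherwise have continued. Whether to go further, for example with a once-daily regimen or compulsory discontinuation after severe events, is a clinical choice and is not needed to close this gap.

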4.4.1.1. Diarrhea

In the event the patient experiences diarrhea, the dose may be reduced. The Common Terminology Criteria for Adverse Events (CTCAE) version 4.0 grading will be used to grade the severity of all AEs and serious adverse events (SAEs) of diarrhea. Management recommendations for diarrhea are based on the CTCAE grades and are detailed in Appendix 2. In general, the patient should be treated with anti-diarrheal drugs such as loperamide as clinically indicated. In addition to directly treating any diarrhea, possible intermittent or permanent interruption of IP and dose reduction will be possible, depending upon the frequency and severity of diarrhea.

4.4.1.2. Aminotransferase (Alanine aminotransferase or Aspartate Aminotransferase) Elevation

Management recommendations for ALT or AST elevations are based on U.S. Food and Drug Administration (FDA) Guidance for Liver Toxicity.

In general, all baseline or treatment-emergent ALT or AST elevations > 3X ULN should be confirmed within 48 to 72 hours with repeat assessments of ALT and AST as well as TBL, alkaline phosphatase (ALP), prothrombin time/INR, and complete blood count for eosinophil levels. Further details for managing IP reduction, restart, and discontinuation can be found in Appendix 3.

If at any time, the criteria as outlined in Section 8 are met, the IP must be permanently discontinued.

4.5. Criteria for Study Termination

This study (including OLE) may be temporarily suspended or prematurely terminated if there is sufficient reasonable cause. Written notification, documenting the reason for study suspension or termination, will be provided by the suspending, or terminating party, to the Investigators, Institutional Review Boards (IRB)/Ethics Committees (EC), regulatory authorities. If the study is prematurely terminated or suspended, the Investigators will promptly inform the IRB/ECs and will provide the reason(s) for the termination or suspension. Circumstances that may warrant termination or suspension include, but are not limited to:

- Determination of unexpected, significant, or unacceptable risk to participants
- Demonstration of efficacy that would warrant stopping
- Insufficient compliance to protocol requirements
- Data that are not sufficiently complete and/or evaluable
- Determination of futility

The study may resume once concerns about safety, protocol compliance, and data quality are addressed and the IRBs/ECs and competent authorities are satisfied. The study will only resume after prior submission and approval of the substantial amendment (if required) by the competent authority.

4.6. Scientific Rationale for Study Design

The design of this study will provide efficacy, safety, and dosing information to support proof of concept. Two rodatristat ethyl doses will be studied. Patients with idiopathic PAH and other Group 1 PAH sub-types will be included in this study.

Placebo-controlled randomized studies provide the most robust results and are thus considered the most appropriate design. However, approved therapies for PAH are available, making a placebo-controlled rodatristat ethyl *monotherapy* study unethical. Therefore, rodatristat ethyl (or placebo) will be evaluated in addition to standard of care (SOC) PAH-specific treatments, i.e., this study will only include patients on stable, approved, and available treatments at baseline.

Patients on prior monotherapy and combination regimens to include up to 3 agents will be permitted to participate. Treatment with oral, inhaled, or parenteral prostanoids will be permitted. Any changes to background PAH therapy during the study should be based on clear medical need.

Protocol RVT-1201-2002

Effective: 19JAN2022

In prior studies of patients treated with PAH therapies, up to 24 weeks of treatment with study medication were considered necessary to demonstrate efficacy based on potential impact on pulmonary hemodynamics. This duration of exposure will also allow for assessment of safety, tolerability, and possible effects on exercise ability, patient reported outcomes, and biomarkers.

The OLE will provide long term safety, tolerability, and efficacy of rodatristat ethyl in patients with PAH. In order to minimize bias during the OLE, patients will remain blinded to original treatment assignment in the Main Study. Patients receiving active rodatristat ethyl during main treatment period will continue at their originally randomized dose to generate additional long-term safety and efficacy data. Patients originally randomized to placebo will also have the opportunity to receive active rodatristat ethyl during the OLE, providing additional patient exposures for further assessment of safety and efficacy.

4.7. Justification for Dose

[figure not shown]
The dose levels selected are based on prior pharmacodynamic (PD) observations in nonclinical models of PAH and PK, PD, safety, and tolerability data in healthy subjects receiving rodatristat ethyl for up to 14 days.

Disease-modifying effects of rodatristat ethyl were demonstrated in the semaxanib (SU5416, SUGEN) hypoxia and the monocrotaline (MCT) injury rat models of PAH. In the MCT rat model, rodatristat ethyl decreased serum and lung 5-HT levels and reduced the extent of vascular remodeling. In the SU5416 hypoxia rat model, rodatristat ethyl significantly reduced RV systolic pressure, RV hypertrophy, the biomarker brain natriuretic peptide (BNP), and pulmonary vessel wall thickness and occlusions as measured by histological analysis, without impacting systolic blood pressure (SBP). These benefits were observed at doses of ≥ 100 mg/kg, which results in approximately a 40% reduction in 5-HT biosynthesis (IB, 2020). Based on these data, a target reduction in 5-HT (as determined by urinary 5-HIAA excretion rate) of at least 40% was the basis for the doses selected in the current study.

After 14 day BID administration to healthy subjects, rodatristat ethyl at doses of 400 to 800 mg BID resulted in 50 to 60% reductions in urinary 5-HIAA. Dose-dependent increases in gastrointestinal treatment-emergent AEs (TEAEs; notably nausea and diarrhea) were noted with rodatristat ethyl, including an event of moderate diarrhea and an overall incidence rate of 44% after administration of 800 mg BID (IB, 2020). Therefore, the highest dose regimen selected for the current study is rodatristat ethyl 600 mg BID which is expected the maintain the majority of the 5-HT lowering effect while minimizing potential of gastrointestinal TEAEs.

The lower dose regimen of rodatristat ethyl of 300 mg BID was selected to evaluate a lower dose to aid in defining potential dose-response relationships and is expected to result in approximately 40% reduction in 5-HIAA, equivalent to the reductions observed at efficacious doses in nonclinical models (IB, 2020).

Figure 2: Percentage Change from Baseline of Urine 5-HIAA: Creatinine Ratio 5-HIAA on Days 7 and 14 following Twice Daily Repeat Oral Administration of Rodatristat Ethyl in Studies KAR5585-101 and RVT-1201-1001

Note: Blue boxes and green boxes represent data from Day 7 and Day 14, respectively. Data for subjects receiving placebo represent totality of data across BID cohorts.

Abbreviations: 5-HIAA = 5-hydroxyindoleacetic acid; BID = twice daily

Aside from the dose-dependent gastrointestinal TEAEs observed in healthy subjects receiving higher doses for 14 days, which have all been considered mild with the exception of 1 event of moderate diarrhea, no other safety concerns were identified following single doses ranging up to 2000 mg or following repeat dosing over 14 days of up to 800 mg administered BID to healthy subjects. The majority of TEAEs for all dose regimens evaluated to date have been mild and have resolved without requiring intervention or discontinuation of the IP. There have been no SAEs reported nor any dose-limiting toxicities identified. Mild, transient elevations in ALT were reported in 5 subjects who received either single or multiple doses of rodatristat ethyl (5 of 136 subjects [3.7%]). Further information can be found in the Investigator's Brochure.

With respect to nonclinical toxicology studies, rodatristat ethyl and rodatristat exposures at the no observed adverse effect level (NOAEL) in the 26-week rat (female only) or 39-week dog toxicology studies are > 4-fold higher than the expected exposure after at the higher dose regimen of 600 mg BID (IB, 2020). Due to adverse decreases in mean body weight gain (20 to -41.7% relative to controls) and food consumption at all dose levels in the 26-week study in male rats, the NOAEL could not be established. Exposure at the lowest dose tested in this study was 4-fold higher than that anticipated at the higher dose regimen of 600 mg BID. The major toxicities associated with oral rodatristat ethyl administration included mortality in rats preceded by clinical signs of toxicity and body weight loss occurring at exposures > 4-fold the highest exposure expected in the current study. Findings in both species were indicative of gastrointestinal changes including decreased body weight and/or decreased rate of weight gain, decreased food consumption, diarrhea/fecal change, dehydration, distended abdomen (rats only),

monitorable.

intestinal dilation with mucosal thickening and macrophage vacuolation (rats only), histopathologic findings of intestinal dilation with vacuolated macrophages, and increased mucosal thickness with regeneration in the duodenum. Observed liver enzyme elevations were not associated with adverse histopathology (hepatocellular necrosis) and are considered

Protocol RVT-1201-2002

Effective: 19JAN2022

Prior studies have demonstrated coadministration of rodatristat ethyl with food can increase systemic exposure of rodatristat ethyl and rodatristat from 1.1- to 1.8-fold. Thus, the prior Phase 1 studies in healthy subjects evaluated rodatristat ethyl administered with a standard meal (IB, 2020). To maintain consistency with these studies and therefore the expected PD effects, IP will be administered BID with a standard meal.

Taken together, the nonclinical pharmacology and safety data, and prior clinical experience with rodatristat ethyl support the low and high BID dose regimens (300 mg and 600 mg) to be evaluated in patients with PAH over the 24-week treatment period.

